11.1.1 Sample Size Justification

We assume a median PFS of 8 months for the INCB024360 alone arm. For the purpose of our simulation study we utilized the simplifying assumption that the covariate adjustment for time between treatment and clinical site are not significant. We also assume a constant hazard rate and a 9 month accrual period with up to 5 years of follow-up. The detectable effect size for the INCB024360 in combination with the DEC205mAB-NY-ESO-1 fusion protein (CDX-1401) arm

different from the INCB024360 alone arm is a PFS of 16 months (or a 2 to 1 risk ratio) with a power estimated from simulation of 0.70. From a practical consideration n = 25 patients per arm is anticipated to be the maximum for which we can accrue during the timeframe of this study.

An additional exploratory cohort (N=6) receiving the same DEC205mAb-NY-ESO-01 fusion protein (CDX-1401) with adjuvant poly-ICLC but in combination with sirolimus in place of INCB024360 will be added to supplement the secondary objectives, which will aid in planning the next phase of the investigation.

11.2 Secondary Objectives

The secondary analysis of continuous immunological response endpoints [antibody titres; NY-ESO-1 specific CD8⁺ and CD4⁺ frequency and function (IFN- γ ELISPOT and tumor recognition by CTL)] will be analyzed in a straightforward analysis-of-covariance (ANCOVA) fashion modeling post-treatment levels as a function of pre-treatment levels with factors corresponding to INCB024360 (yes/no) and DEC205mAb-NY-ESO-1 fusion protein (CDX-1401) with adjuvant poly-ICLC (yes/no).

Similarly, for the exploratory cohort at Roswell site only, the secondary analysis of continuous immunological response endpoints [antibody titres; NY-ESO-1 specific CD8⁺ and CD4⁺ frequency and function (IFN- γ ELISPOT and tumor recognition by CTL)] will be analyzed in a straightforward analysis-of-covariance (ANCOVA) fashion modeling post-treatment levels as a function of pre-treatment levels with factors corresponding to sirolimus (yes/no) and DEC205mAb-NY-ESO-1 fusion protein (CDX-1401) with adjuvant poly-ICLC (yes/no).

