Statistical Analysis	
• Phase I: The following decision rules will be followed: (i) If 0/3 dose limiting toxicities (DLTs) are observed proceed to enroll 3 more patients (ii) If 1/3 DLTs are observed enroll 3 more patients at the same treatment regimen. If 0/6 or 1/6 DLTs are observed, declare the regimen safe and as the maximum tolerated dose combination (MTD) of INCBO24360 in combination with the vaccine. If at least 2/3 or 2/6 DLTs are observed in Cohort 1, stop and de-escalate INCBO24360 to 100 mg BID in Cohort -1. If at least 2/3 or 2/6 DLTs are observed in Cohort -1, stop and de-escalate INCBO24360 to 50 mg BID in Cohort -2.• Phase IIb:• The Phase IIb component of this trial will consist of a randomized parallel design of n=25+25=50 patients =50 patients with treatment arms: (i) DEC205mAb-NY-ESO-1 fusion protein (CDX-1401) with adjuvant poly-ICLC alone and (ii) INCBO24360 in combination with the DEC205mAb-NY-ESO-1 fusion protein (CDX-1401) with adjuvant poly-ICLC. Stratification will be on clinical site (Roswell Park, U. of Pittsburgh). The primary endpoint will be progression free survival. Baseline is defined as the time following the treatment free interval, which can span 0 - 2 months, as described in Iasonos et al.[1] The primary analysis will be carried forth using a Cox proportional hazards model with factors corresponding to treatment and a continuous covariate adjustment for the length of the treatment free interval and a stratification factor for clinical site.• Phase I/IIb: The secondary analysis of continuous immunological response endpoints [antibody titers; NY-ESO-1 specific CD8⁺ and CD4⁺ frequency and function (IFN-γ ELISPOT and tumor recognition by CTL)] will be analyzed in a straightforward analysis-of-covariance (ANCOVA) fashion modeling post-treatment levels as a function of pre-treatment levels with factors corresponding to INCBO24360 (yes/no) and DEC205mAb-NY-ESO-1 fusion protein with adjuvant poly-ICLC (yes/no).• Exploratory Cohort: The analysis of continuous immunological response endpoints (e.g., antibody titers; NY-ESO-1 specific CD8⁺ and CD4⁺ frequency and function; frequency of memory T cell populations; TCR avidity) will be analyzed via an analysis-of-covariance (ANCOVA) fashion modeling post-treatment levels as a function of pre-treatment levels with factors corresponding to Sirolimus (yes/no) and DEC205mAb-NY-ESO-1 fusion protein with adjuvant poly-ICLC (yes/no).

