An additional exploratory cohort (N=6) receiving 4 cycles of sirolimus in combination with DEC205mAb-NY-ESO-01 fusion protein (CDX-1401) with adjuvant poly-ICLC will be added to supplement the secondary objectives, which will aid in planning the next phase of the investigation. This will not affect the randomized component of the study as enrollment to the randomized Phase IIb at Roswell Park only will be suspended temporarily until the 6 patients are enrolled. Data will be included as described in Section 11.4 for immune response.

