6.2 Cohort Management

A patient will be considered to have completed treatment with study medications following completion of 7 cycles of treatment and the final assessments at treatment discontinuation. An eligible patient receiving at least 1 dose of the investigational agents, DEC205mAb-NY-ESO-1 fusion protein (CDX-1401) given with adjuvant poly-ICLC with or without INCBO24360, will be considered evaluable for safety. A patient that completes 2 or more cycles of treatment will be eligible for the analysis of immune response. Patients who do not complete the study through Day 29 for reasons other than dose limiting toxicities (DLTs) will be replaced. All patients will be included in the analysis of results.

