11.4 Immune Response

Patients that complete 2 or more cycles of treatment will be eligible for the analysis of immune response.

Due to the early stage of this study and the feasibility considerations, the sample size for this study will be restricted. The analysis of continuous immunological response endpoints (e.g., antibody titers; NY-ESO-1 specific CD8+ and CD4+ frequency and function; frequency of memory T cell populations; TCR avidity) will be analyzed via an analysis-of-covariance (ANCOVA) model with post-treatment levels modeled as a function pre-treatment levels and main effects to the parallel design.

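### The sirolimus immune-response ANCOVA has no contrast to estimate, the vaccine factor is constant in every cohort, and the model omits the randomisation stratum

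*Combined protocol and SAP*

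**What the plan says.** **Main immune model.** Section 11.2 specifies an ANCOVA of post-treatment on pre-treatment level with "factors corresponding to INCB024360 (yes/no) and DEC205mAb-NY-ESO-1 fusion protein (CDX-1401) with adjuvant poly-ICLC (yes/no". The synopsis gives the same two factors under the label "Phase I/IIb: The secondary analysis of continuous immunological response endpoints". Section 11.4 describes the model differently: "post-treatment levels modeled as a function pre-treatment levels and main effects to the parallel design".

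**Sirolimus cohort.** Section 11.2 applies the same form to the six Roswell Park patients, with "factors corresponding to sirolimus (yes/no") and again the vaccine factor. On these patients Section 3.1 says "Data will be included as described in Section 11.4 for immune response". Section 11.4 does not mention sirolimus. Section 3.1 also says that "enrollment to the randomized Phase IIb at Roswell Park only will be suspended temporarily until the 6 patients are enrolled".

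**Analysis set.** Sections 6.2 and 11.4 agree: "Patients that complete 2 or more cycles of treatment will be eligible for the analysis of immune response".

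**Site.** Section 11.1 stratifies randomisation by clinical site (blocks of 4, 1:1) and carries site into the primary Cox model. No description of the immune ANCOVA includes it.

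**Sampling.** Section 7.5 lists blood draws on Day 1 of Cycles 1 to 5, at treatment discontinuation, and 3, 6 and 12 months after the last vaccine or the last INCB024360 dose. None is named as the post-treatment value for the ANCOVA.

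**The concern.** The secondary objective asks whether INCB024360, and in the exploratory cohort sirolimus, enhances vaccine immunity. The sirolimus data are also meant to help plan the next phase.

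As written, the sirolimus model cannot be fitted on its own cohort. Two analysts could choose different control groups, reach different answers, and both claim to have followed the plan. The main model carries a term that cannot be estimated and leaves out the factor used to stratify randomisation. The texts also leave it to the analyst whether Phase I patients enter the model and which sample is the outcome.

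**Working it through.** The plan states no sample size, alpha or power for the immune ANCOVA, so there is no figure to reproduce. The check is of the model itself.

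**1. Main model.** Inputs: Table 1 gives the vaccine to all Phase I cohorts and both Phase IIb arms, Table 2 gives it to the sirolimus cohort, and the 2-cycle rule excludes anyone unvaccinated. The design columns are [1, pre-treatment level, INCB024360, vaccine]. Vaccine = 1 for everyone, so the fourth column equals the first.
- Rank for Phase IIb alone (n = 50): 3 of 4. The vaccine effect cannot be estimated.
- Fitted to simulated data with and without the vaccine column, the INCB024360 coefficient is identical (0.4635 both ways).

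**2. Sirolimus model, six patients.** The columns are [1, pre-treatment level, sirolimus = 1, vaccine = 1]. Three of the four are identical, so the rank is 2 of 4 and there is no sirolimus contrast. Adding the 25 vaccine-alone patients of Cohort 2a (n = 31) raises the rank to 3 of 4: sirolimus becomes estimable, vaccine still does not.

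Precision, assuming two-sided 0.05, 80% power and residual SD 1: detectable difference = (1.960 + 0.842) × √(1/6 + 1/c) for c controls.
- c = 25 (all of Cohort 2a): 2.802 × 0.455 = 1.27 SD
- c = 13 (assumed Roswell Park share): 2.802 × 0.494 = 1.38 SD
- c = 8 (assumed Roswell Park share): 2.802 × 0.540 = 1.51 SD

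**3. Site.** With all 50 randomised patients, adding site takes the residual degrees of freedom from 50 − 3 = 47 to 46. The two-sided 5% critical value goes from 2.012 to 2.013.

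**4. Phase I, if pooled.** The note to Table 1 says 300 mg BID was selected, and Section 11.1 de-escalates from Cohort 1 only after at least two DLTs, so Cohort 1 alone was presumably used. Section 11.1 declares a regimen safe at 0/6 or 1/6. Section 6.3.1 takes a patient with a DLT in the first 28 days off treatment (with an exception for hypersensitivity), so at 1/6 about five patients would meet the 2-cycle rule. All would have INCB024360 = yes.
- Share of the yes group: 5/(25 + 5) = 17%; 6/(25 + 6) = 19%.
- A Phase I versus Phase IIb difference of d would move the contrast by about 0.17d to 0.19d. The documents give no value for d.
- Standard error of the arm contrast without pooling relative to with it, √(2/25) / √(1/25 + 1/(25 + k)): 1.044 for k = 5 and 1.052 for k = 6.

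**5. Which sample.** Taking Cycle 1 Day 1 as baseline (assumed drawn before dosing), eight samples follow. Four are at or after treatment discontinuation; the other four are on treatment. On schedule the last CDX-1401 dose is on Day 4 × 28 + 1 = 113 and the last INCB024360 dose on Day 7 × 28 = 196. If each arm is dated from its own last drug, the 3, 6 and 12 month samples fall 196 − 113 = 83 days apart between arms.

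**The case against.** The strongest reply is that these are clarifications to secondary and exploratory analyses with no alpha or decision rule attached. Much of it stands.

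- **Vaccine factor.** A reader might infer that it invalidates the INCB024360 comparison. It does not: software drops the column and the estimate is the same.
- **Pooling.** A reader might infer that Phase I will be pooled. The documents do not say so. The only parallel design in the protocol is Phase IIb, so Section 11.4 points to randomised patients only, and the synopsis label may just echo the heading of the shared secondary objectives. The shift in step 4 is conditional on a reading that is not the natural one.
- **Site.** A reader might infer a biased comparison. Blocks of 4 within site keep the arms within two patients of each other at each site, so confounding is small. The case for the term is consistency with the randomisation and the Cox model.
- **Visits.** A reader might infer a free choice among eight samples and a false-positive rate of 1 − 0.95^8 = 0.34. That counts on-treatment samples as post-treatment, treats correlated repeat samples as independent, and assumes a 5% test that the plan does not state. Section 6.2, which counts completion as seven cycles with or without INCB024360, can also be read as aligning the timing of the two arms.
- **Sirolimus comparator.** Section 11.1.1 describes sirolimus as replacing INCB024360 with the same vaccine, which points to vaccine-alone patients. Reading the no group as everyone else would bring in 25 INCB024360 patients among the 50 randomised with no term for that drug, but it is the less plausible reading.

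What the reply does not remove: no text names the sirolimus comparator, and the section to which Section 3.1 refers does not supply one. The inestimable term and the missing stratum also remain in the written model.

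**Conclusion.** The immune-response ANCOVA is mis-specified and should be corrected. In order of weight:

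1. The sirolimus model has no contrast within its cohort (rank 2 of 4) and no named comparator.
2. The vaccine factor cannot be estimated in any cohort. This is a wording error with no effect on the INCB024360 estimate.
3. Site is missing from the model, with little expected bias.
4. The pooling of Phase I and the post-treatment sample need aligned wording. About 5 or 6 non-randomised patients, on one side only, are at issue for the first. Four candidate samples (eight if on-treatment draws count) are at issue for the second.

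Points 1 to 3 follow directly from the text. Point 4 rests on assumptions: that Cohort 1 was the only Phase I cohort used, that pooling was contemplated at all, and that the late samples are dated separately by arm. The PFS analysis is untouched.

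**What to change.** In the synopsis, Section 11.2 and Section 11.4, state one model on randomised Phase IIb patients who meet the 2-cycle rule: post-treatment level on Cycle 1 Day 1 level, randomised arm and site. Delete the vaccine factor. Report Phase I separately.

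Name in advance one sample taken at the same time from first vaccination in both arms, with the others as supportive. If an on-treatment sample such as Cycle 5 Day 1 is chosen, say that it is on treatment (after 112 of the 196 scheduled INCB024360 days) and whether blood is drawn before that day's vaccine, which Section 7.5 does not state. That choice changes the quantity estimated.

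For sirolimus, name the Roswell Park patients of Cohort 2a as comparator and report the comparison descriptively. State that they were not randomised against the six and are largely non-concurrent, because randomisation at that site is suspended while the six enrol.

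Cost: no new visits or samples, one residual degree of freedom for site, and a standard error about 4% to 5% wider only if pooling had been intended.

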11.3 Toxicity

All patients enrolled in this study will be eligible for the analysis of toxicity.

The toxicity rate will be estimated using a one-sided, 95%, exact binomial confidence interval (Clopper-Pearson). The lower one sided limit will be used.

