6.1.5 Compliance

CDX-1401 and poly-ICLC will be administered by the study staff on the CDX-1401 dosing dates, and may be self-administered by the patient for the remaining doses. Compliance with self-administration of adjuvants and INCB024360 (or Sirolimus for exploratory cohort) will be assessed via patient-reported dosing diaries (**Appendix C** and **Appendix D**).

Table 1. Dosing Schedule for INC024360 and DEC205mAb-NY-ESO-1 Fusion Protein (CDX-1401) Given with Adjuvant Poly-ICLC

Treatment Cohorts	Number of Patients	DEC205mAb-NY ESO 1 Fusion Protein (CDX 1401) Given with Adjuvant Poly-ICLC ^a	INC024360 (Oral)
Phase I			
Cohort -2	3 – 6 patients	
 • DEC205mAb-NY-ESO-1 fusion protein (1 mg, intracutaneous injection) on Day 1 of each 28 day cycle for a total of 5 cycles. • Adjuvant poly-ICLC (1 ml, subcutaneous) on Day 1 and Day 2 of each 28 day cycle for a total of 5 cycles. 	50 mg BID for a total of 7 cycles
Cohort -1	3 – 6 patients	
 • DEC205mAb-NY-ESO-1 fusion protein (1 mg, intracutaneous injection) on Day 1 of each 28 day cycle for a total of 5 cycles. • Adjuvant poly-ICLC (1 ml, subcutaneous) on Day 1 and Day 2 of each 28 day cycle for a total of 5 cycles. 	100 mg BID for a total of 7 cycles
Cohort 1 (start)	3 – 6 patients	
 • DEC205mAb-NY-ESO-1 fusion protein (1 mg, intracutaneous injection) on Day 1 of each 28 day cycle for a total of 5 cycles. • Adjuvant poly-ICLC (1 ml, subcutaneous) on Day 1 and Day 2 of each 28 day cycle for a total of 5 cycles. 	300 mg BID for a total of 7 cycles
Randomized Phase IIb (parallel groups design)			
Cohort 2a	25 patients	
 • DEC205mAb-NY-ESO-1 fusion protein (1 mg. intracutaneous injection) on Day 1 of each 28 day cycle for a total of 5 cycles • Adjuvant poly-ICLC (1 ml. subcutaneous) on Day 1 and Day 2 of each 28 day cycle for a total of 5 cycles.. 	None
Cohort 2b	25 patients	
 • DEC205mAb-NY-ESO-1 fusion protein (1 mg, intracutaneous injection) on Day 1 of each 28 day cycle for a total of 5 cycles. • Adjuvant poly-ICLC (1 ml, subcutaneous) on Day 1 and Day 2 of each 28 day cycle for a total of 5 cycles. 	300 mg BID for a total of 7 cycles

1 Refer to **Section 11** statistical considerations and additional decision rules.

Based on phase 1 safety review, INC024360 300 mg. po BID for a total of 7 cycles was determined the phase IIb dose level.

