6.3.1 Definition of Dose-Limiting Toxicity

Patients who do not complete the study through Day 29 for reasons other than dose limiting toxicities (DLTs) will be replaced. All patients will be included in the analysis results.

All AEs (as defined in **Section 9**) will be graded according to the NCI-CTCAE scale Version 4.0. Patients who experience a DLT will not receive any additional treatment (i.e., will be removed from the study and followed until resolution of their toxicity) and will not receive continued treatment even at a reduced dosage of the INCB024360 product. Patients with dose limiting toxicities requiring drug discontinuation (specified below) will be removed from the study (see exception for hypersensitivity reaction). The DLT period will be defined as 28 days after the first dose of vaccine. Late developing toxicities, occurring between Day 29 and Day 183 will be monitored throughout the study and according to the schedule of procedures and observations. Patients may be withdrawn from study even if DLT is due to INCB024360 or sirolimus alone. Safety monitoring will include careful assessment and appropriate reporting of AEs, as well as the construction and implementation of a data and safety-monitoring plan (Auditing, Monitoring, and Inspecting). Medical monitoring will include a regular assessment of the number and type of SAEs. Refer to the stopping rules for this study in **Section 6.3.2**. Any event(s) that might appear to trigger a treatment discontinuation rule or trial stopping rule will be discussed with the FDA review team. For phase IIb dose reductions for INCB024360 will be allowed (see section 6.3)

Management and dose modifications associated with AEs are outlined in **Section 6.3**. Refer to **Section 11** for statistical considerations and additional decision rules.

These events should be deemed to be possibly, probably or definitely related to study drugs. DLT criteria will be defined as any Grade 3 or higher treatment-related (i.e. definitely, probably, or possibly related) toxicity that occurs during the DLT evaluation period, including:

- Febrile neutropenia with standard of care treatment for ≥ 7 days. Growth factors may be used according to American Society of Clinical Oncology guidelines.
- Platelets $\leq 50 \times 10^9/L$
- Grade 3 or greater non-hematologic toxicity
- New onset pulmonary hypertension, interstitial pneumonitis or, CNS bleeding
- Serum bilirubin $> 3.0 \text{ mg/dL}$

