11.5 Interim Analysis and Criteria for Early Termination of the Study

All patients enrolled in this study will be eligible for the analysis of safety.

Drug safety will be monitored and evaluated weekly throughout the study including a 30 day safety follow-up period by obtaining, reviewing and analyzing data on AEs, changes in laboratory values, vital signs, and physical examination findings. If the committee views the toxicity as unacceptable, the trial will be stopped early.

In the phase 2 portion of the study, the Roswell Park Data Safety Monitoring Committee will assess the progress of the study, the safety data, and critical efficacy endpoints. The DSMC will review the study annually and will make recommendations that include but not limited to; (a) continuation of the study, (b) modifications to the design (c) or termination of the study.

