3. STUDY DEVIATIONS

- If a deviation has occurred to eliminate hazard, this must be reported to the Roswell Park Network, site IRB and any other regulatory authority involved in the trial.
- All study deviation will be recorded on the **Study Deviation Log**.
- Subjects inadvertently enrolled with significant deviation(s) from the study-specified criteria will be removed from the study.

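### Section 11.3 plans only a lower one-sided limit for the toxicity rate, so the planned interval always ends at 100% and cannot show how high toxicity could be

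*Combined protocol and SAP*

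**What the plan says.** The whole interval plan for toxicity is in the second paragraph of section 11.3: "The toxicity rate will be estimated using a one-sided, 95%, exact binomial confidence interval (Clopper-Pearson). The lower one sided limit will be used". The paragraph before it sets the population: "All patients enrolled in this study will be eligible for the analysis of toxicity". Section 11.3 names no cohort or arm as the denominator and no grade or attribution as the event.

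Safety and CTCAE toxicity are the Phase I primary objectives (section 2.1). The other safety provisions work without this interval:

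- Section 11.1 makes the Phase I dose decision from counts of dose-limiting toxicities (DLTs), with 0/6 or 1/6 leading to a declaration of safety. For these, "The DLT period will be defined as 28 days after the first dose of vaccine" (section 6.3.1). The decision has been taken: the note to Table 1 records that 300 mg BID "for a total of 7 cycles was determined the phase IIb dose level".
- Section 6.3.2 pauses the study for any Grade 4 event and suspends accrual for a treatment-related death or a related Grade 4 event.
- Section 6.3 lists Phase IIb dose-modification criteria, based on Grade 3 or higher related toxicity outside the DLT period.
- Sections 10 and 11.5 provide committee review. Section 11.5 sets no numerical rate: "If the committee views the toxicity as unacceptable, the trial will be stopped early".

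**The concern.** A safety estimate has to answer one question above all: given what was seen, how high could the true rate be? A lower limit answers a different one, namely how low it could be. That is useful when the plan names an unacceptable rate and wants to show that toxicity exceeds it. Here no such rate is named and no rule refers to the limit.

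The other provisions do not supply the missing estimate. The DLT-count rule covers the Phase I INCB024360 cohorts over 28 days, whereas planned INCB024360 treatment lasts 7 × 28 = 196 days. The Phase IIb arms (25 each) and the sirolimus cohort (6) lie outside that rule. The 11.3 limit is the only interval estimate of a toxicity rate planned for any part of the trial.

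At stake is how the safety results read. With few events, the one bound that is reported is close to zero and always at or below the observed rate, so it errs in the reassuring direction.

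**Working it through.** Section 11.3 gives no numerical limit, so there is no plan figure to reproduce. The check computes what the planned limit would be and what it leaves out.

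**Inputs.** Method, level and side: section 11.3. Cohort of 6: the Phase I decision rule in 11.1 and the exploratory cohort in 11.1.1. Arm of 25 and total of 50: Phase IIb in 11.1. *Assumptions:* counting by cohort or arm, and the event counts x, which are illustrations.

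**Formulas (Clopper-Pearson, x events in n).**

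- Lower one-sided 95% limit: the 0.05 quantile of Beta(x, n − x + 1), and 0 when x = 0.
- Upper one-sided 95% limit: the 0.95 quantile of Beta(x + 1, n − x).
- Two-sided 95% interval: the same with 0.025 and 0.975.

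Two cases can be done by hand:

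- With x = 0 the upper limit is 1 − 0.05^(1/n): n = 6 gives 0.393, n = 25 gives 0.113, n = 50 gives 0.058.
- With x = 1 the lower limit is 1 − 0.95^(1/n): n = 6 gives 0.0085, n = 25 gives 0.0020.

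**Results.**

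| x/n | Lower one-sided (planned) | Upper one-sided (omitted) | Two-sided 95% |
|---|---|---|---|
| 0/6 | 0% | 39.3% | 0–45.9% |
| 1/6 | 0.85% | 58.2% | 0.4–64.1% |
| 0/25 | 0% | 11.3% | 0–13.7% |
| 1/25 | 0.2% | 17.6% | 0.1–20.4% |
| 5/25 | 8.2% | 37.5% | 6.8–40.7% |
| 0/50 (arms pooled) | 0% | 5.8% | 0–7.1% |

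**Reading the table.**

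1. With no events the planned interval is 0–100% at any sample size. It cannot tell 0/25 from 0/6, although the upper limits are 11.3% and 39.3%.
2. After 5 events in 25 the observed rate is 20%. The planned figure is 8.2%, while rates up to 37.5% remain compatible with the data.
3. These counts suit an uncommon event such as Grade 3 or higher related toxicity. For a common event the picture differs. Section 1.6.1.2 reports injection site reactions in 76% of earlier CDX-1401 patients. As an illustration, 0.76 × 25 = 19, and 19/25 gives a lower limit of 58.0%, which is informative. The upper limit of 89.0% would still go unreported.

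**The case against.** The strongest reply is that nothing decided in the trial depends on this limit. The dose has been chosen from DLT counts, accrual is paused or suspended by individual events, Phase IIb doses are modified on stated criteria, and committees review safety. Once x and n are published, any reader can compute an upper limit, so no information is lost. All of that stands, and it caps the size of the point. It does not make the planned bound the right one for a safety objective.

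A second reply is that the authors may have meant an interval from 0 up to an upper limit. The text names the lower limit, so that reading needs the same edit.

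A reader might also infer more than the documents support:

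- *That the interval is uninformative whatever is observed.* Only its upper end is fixed. L varies, and for common events it carries information. The 0–100% case needs zero events, which is realistic only for rare, severe toxicity.
- *That treated patients later found ineligible would drop out of the toxicity analysis.* Section 6.2 does describe safety evaluability by "An eligible patient receiving at least 1 dose of the investigational agents", and the Study Deviations part of the network-site instructions says "Subjects inadvertently enrolled with significant deviation(s) from the study-specified criteria will be removed from the study". But 6.2 and 6.3.1 each add that every patient goes into the analysis, and 11.5 agrees with 11.3: "All patients enrolled in this study will be eligible for the analysis of safety". Removal from the study is not removal of safety data. What remains is a mismatch of wording between enrolment (11.3, 11.5) and receipt of at least one dose (6.2).
- *That toxicity is undefined.* CTCAE Version 4.0 (2.1), Grade 3 or higher with possible, probable or definite attribution (6.3, 6.3.1), and reporting by grade and attribution (9.1.3) are all there. Only a link from 11.3 to one of them is missing.

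**Conclusion.** The point holds as a fault in safety estimation and reporting, and it should be fixed. As written, 11.3 reports the bound that cannot limit toxicity from above, and no stated threshold gives a lower limit a purpose. The gap is largest where events are few: 0% reported against an upper limit of 39.3% for 0/6 and 11.3% for 0/25, and 8.2% against 37.5% for 5/25.

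These sizes rest on two assumptions that 11.3 does not settle: counting by cohort or arm, and an uncommon event. Pooling the Phase IIb arms would narrow the zero-event gap to 0% against 5.8%. Under either denominator, and for common as well as rare events, the planned interval still ends at 100%.

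A reader might conclude that the dose selection or the stopping provisions are unsound because of this. The documents do not support that, since none of those rules uses the 11.3 limit.

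**What to change.** Replace the two sentences of the second paragraph of 11.3 with:

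*For each cohort and treatment arm the toxicity rate will be reported as x/n with the two-sided 95% Clopper-Pearson interval (or the upper one-sided 95% limit).*

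In the same edit, refer 11.3 to an event definition that the protocol already contains; the sponsor should say which. If wanted, align the population wording of 11.3 and 11.5 with that of 6.2.

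The cost is a few sentences and no new data. The reported bound becomes less favourable. By-arm intervals are wider than pooled ones (upper one-sided limit 11.3% for 0/25 against 5.8% for 0/50), and the two-sided upper limit is higher than the one-sided one (13.7% against 11.3% for 0/25).
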